## 15.2. APPENDIX 2: STATISTICAL ANALYSIS CONVENTIONS

### 15.2.1. Conventions for calculation of duration

#### 15.2.1.1. Calculation of a duration in months or years

Duration in years or months (i.e. treatment duration, duration of follow-up, disease and treatment free intervals, time from diagnosis to study entry, time to first response, duration of response, stabilisation and disease control, PFS and overall survival) will be calculated as follows :

$$\text{Duration (in months)} = \frac{(\text{Date 2} - \text{Date 1}) + 1}{30.4375}$$

with Date 2 • Date 1.

$$\text{Duration (in years)} = \frac{(\text{Date 2} - \text{Date 1}) + 1}{365.25}$$

For example, age of the patients will be calculated as follows :

$$\text{Age (in years)} = \frac{(\text{Date of registration} - \text{Date of birth}) + 1}{365.25}$$

#### 15.2.1.2. Calculation of a delay or time duration in days

Delays or time durations, usually in days, (i.e. number of days of delay in a cycle, delay between randomisation and first administration, number of days between last administration or visit and death, delay between diagnosis and study entry, delay between diagnosis and progression, time from randomisation to first concomitant radiotherapy) will be calculated as follows :

$$\text{Delay (in days)} = \text{Date 2} - \text{Date 1}$$

with Date 2 • Date 1.

### 15.2.2. Missing data

#### 15.2.2.1. General conventions

Following internal biometry conventions are used:

- "M" stands for an information not present on CRF form,

### **15.2.2.2. Conventions for dates**

For dates, if the day is missing then convention is to put the day to the value of 15 (half of the month). If the day and the month are missing then convention is to put the day to the value of 01 and the month to the value of 07 (half of the year). This convention allows to approximate some delays (mostly delays analysed at baseline).

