## 4.1. PRIMARY EFFICACY PARAMETERS

### 4.1.1. Overall survival

The primary efficacy parameter is overall survival defined as the time from randomization to the date of death or last follow-up. For patients who have not died, survival duration will be censored at the date of last contact or last follow-up.

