### **5. SAFETY PARAMETERS**

#### **5.1. ADVERSE EVENTS**

Each patient will be assessed for occurrence of adverse events. The CTCAE version 3.0 (publish date 9 Aug 2006) will be used. Adverse events not classified by the CTCAE will also be reported and graded according to their severity: mild (grade 1), moderate (grade 2), severe (grade 3), life-threatening or disabling (grade 4), sudden death (grade 5), not applicable in case of progression or adverse event not gradable according to CTCAE and leading to dose modification (NA).

Treatment Emergent Adverse Events (TEAE) will be considered for analysis of adverse events. A TEAE is defined as any event that first occurred during the treatment period (i.e. from first drug administration date up to last administration date + 30 days) or that “worsened” during that study period. The definition of “worsening” is described below:

- Any increase in the grade (according to CTCAE) compared to baseline sign or symptom, or
- Any sign or symptom becoming serious during the study period, or
- Any sign or symptom requiring a modification of the study drug administration, or
- Any sign or symptom becoming possibly, probably or definitely related to the study drug

An adverse event that meets one of the criteria described above will be considered as TEAE and reported in the analyses for the remainder of the study, even if the TEAE downgrades to baseline situation.

Baseline situation of the pre-treatment adverse events will be determined by using:

- the worst grade of the adverse events during the pre-study period (within 2 weeks prior to treatment),
- the seriousness of the event during the pre-study period,

This situation will be used as comparator to determine whether an existing adverse event during study period becomes treatment-emergent.

The adverse events will be classified using the Medical Dictionary for Regulatory Activities (MedDRA). The implementation of this international terminology in the Oracle Clinical® database will be performed using the available version of MedDRA (Version 19.0). Each description of the toxicity (verbatim) will be associated with the five following items:

- System Organ Class (SOC),
- High Level Group Term (HLGT),
- High Level Term (HLT),
- Preferred Term (PT),
- Lowest Level Term (LLT).

Two sets of events will be considered:

- all adverse events regardless of relationship to treatment,
- the adverse events that are possibly, probably or definitely related to treatment,

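### The SAP's only partial-date rule has no floor, so it can date an on-treatment adverse event before first dose, or a death before randomisation or the last date known alive

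*SAP*

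**What the plan says.** SAP 15.2.2.2 has two rules. The first is "For dates, if the day is missing then convention is to put the day to the value of 15". The second begins "If the day and the month are missing then convention is to put the day to the value of 01" and sets the month to July. On scope it adds only "This convention allows to approximate some delays (mostly delays analysed at baseline". Neither document has another rule for incomplete dates. SAP 15.2.3 says which of several assessment dates to take for response or progression, not how to complete a partial one.

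Two definitions depend on these dates:

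- **Adverse events (SAP 5.1).** "Treatment Emergent Adverse Events (TEAE) will be considered for analysis of adverse events". Further, "A TEAE is defined as any event that first occurred during the treatment period", that is, "from first drug administration date up to last administration date + 30 days". An event with an earlier onset still qualifies if it worsens. Worsening means a higher grade than at baseline, becoming serious, needing a change to study drug administration, or "Any sign or symptom becoming possibly, probably or definitely related to the study drug". Missing causality counts as related.
- **Overall survival (SAP 4.1.1).** It is "defined as the time from randomization to the date of death or last follow-up". SAP 15.2.1.1 computes it as ((Date 2 - Date 1) + 1)/30.4375. The condition linking the two dates has lost its sign in the text available here; presumably Date 2 must not precede Date 1.

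**The concern.** A mid-point is a reasonable guess for a diagnosis date years before the study. It is less safe for a date near a boundary that decides how the record is classified. First dose is such a boundary for adverse events, and randomisation is one for survival. The 15th, or 1 July, can fall on the wrong side of either, and the SAP sets no lower limit.

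The word *mostly* in the scope sentence does not confine the rule to baseline. SAP 15.2.1.2 includes post-randomisation intervals among its delays, such as last administration to death and randomisation to first concomitant radiotherapy.

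At stake are some early adverse events missing from the treatment-emergent tables and, in rare cases, a survival time that is negative or shorter than follow-up already recorded. A misplaced death date would also affect the split between deaths within and beyond 30 days of last dose (SAP 11.2.4) and the toxic-death definition (SAP 15.2.4.3).

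**Working it through.** The plan gives no figure to reproduce here, so the check is calendar arithmetic.

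**Inputs.** The imputation rule is SAP 15.2.2.2 and the duration formula SAP 15.2.1.1. Recruitment stopped on 16 October 2015 (SAP 1). Planned median survival is 5.5 and 7.5 months (SAP 3).

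**Assumptions.** Entry starts on 1 January or 15 February 2014 (the protocol synopsis says only Q1 2014). Entry dates are evenly spread, survival is exponential, and deaths are counted to 5 February 2016, the date of amendment PA11 (SAP 13).

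**Examples.**

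| Case | True | Imputed |
|---|---|---|
| First dose 20 Mar 2015, onset 25 Mar, day missing | 5 days after first dose | 15 Mar, 5 days before first dose |
| Randomised 20 Mar 2015, died 29 Mar, day missing | (9+1)/30.4375 = 0.33 months | (-5+1)/30.4375 = -0.13 months |
| Randomised 10 Sep 2014, died 20 Nov 2014, year only | (71+1)/30.4375 = 2.37 months | 1 Jul: (-71+1)/30.4375 = -2.30 months |

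**Adverse events with the day missing, in the month of first dose.** If first dose is on day d of a 30-day month, 31 - d days of that month are on treatment. The imputed date precedes first dose only when d is 16 or later. With onset evenly spread from first dose to month end, the share misplaced is

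(15 + 14 + ... + 1)/(30 + 29 + ... + 1) = 120/465 = 26%.

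The actual calendar gives the same 26% from either start date. By true lag, over start dates from 1 January 2014, the chance is 46% one day after first dose, 27% at 7 days, 5% at 14 days and zero at 21 days.

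**The reverse error.** Take true onsets 1 to 14 days before first dose in the same month. The 15th falls on or after first dose when d is 15 or earlier. Counting day pairs:

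- d = 2 to 15 gives 1 + 2 + ... + 14 = 105, all moved into the treatment period.
- d = 16 to 30 gives 15 x 14 = 210, none moved.

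The share moved is 105/315 = 33%.

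**Deaths with the day missing.** The imputed date precedes randomisation only if the patient is randomised after the 15th and dies in the same month. About half of patients are randomised after the 15th, with on average 8 days of the month left (the mean of 15, 14, ..., 1). With daily hazard ln 2/(median x 30.4375), the share of patients is

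- median 5.5: 0.5 x (1 - exp(-0.00414 x 8)) = 1.6%
- median 7.5: 0.5 x (1 - exp(-0.00304 x 8)) = 1.2%.

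The full calendar calculation gives 1.7% and 1.2%. As a share of deaths by the cut-off (about 78% and 69% of patients with the January start), this is about 2%.

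**Deaths with only the year known.** The imputed date precedes randomisation if the patient is randomised after 1 July and dies in the same year. That is about 15% of patients at a median of 5.5 months and 12% at 7.5. Among deaths by the cut-off it is 17-21% across both medians and both start dates. The mean absolute error is about 92 days.

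**The case against.** The case against is substantial.

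- The scope sentence shows that the authors had baseline intervals in mind.
- A misdated event is not automatically lost. The worsening criteria, with missing causality counted as related, restore related, serious, dose-modifying or higher-grade events. Haematology and biochemistry are graded from laboratory data (SAP 5.3 and 5.4).
- The event stays visible elsewhere. Pre-treatment events are tabulated separately, the summary table counts all adverse events beside treatment-emergent ones, and every record is listed.
- Early deaths are the least likely to lack a day. On-treatment deaths are serious adverse events notified within 24 hours on a form with day, month and year (Protocol 9.2 and Appendix 5). Until PA11, survival contact was monthly for six months after progression and then three-monthly (Protocol 7.7).
- Consistency checks with queries are planned (Protocol 13.2), and a death before randomisation would very probably be queried.

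All of this stands and lowers the likely number of affected records. None of it supplies a rule for a date that stays incomplete after querying.

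Three stronger readings are tempting and are not supported:

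- *Half of early adverse events are lost.* About half of first doses fall after the 15th, but a late first dose leaves few on-treatment days in that month. Per event the figure is about 26%, before any recovery through the worsening criteria.
- *The error only removes events.* True pre-dose events also move into the treatment period, as the 33% above shows.
- *The survival result is compromised.* The 17-21% applies only to deaths dated by year alone, and nothing in the documents suggests that there are many.

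**Conclusion.** The point holds as a minor one. SAP 15.2.2.2 is unrestricted, stands alone and has no floor, so applied literally it can give an impossible or misclassified date. The adverse events really exposed are mainly non-serious, unrelated events without dose change, with onset in the month of first dose (or in the same year, if only the year is known). For deaths the size is about 2% of those with a missing day and 17-21% of those dated by year only. These figures rest on the assumed entry dates, exponential survival and cut-off, and are conditional on the date being partial. The number of partial dates is not given and is probably small, so no material effect on the survival comparison or the safety conclusions is claimed.

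**What to change.** Keep the mid-point convention in SAP 15.2.2.2 and add floors:

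- **Adverse events.** For an event recorded as starting on or after treatment (not as a pre-treatment event), impute onset no earlier than first dose. Apply this only when the known month or year includes first dose and the mid-point falls before it. A mid-point after first dose stands.
- **Death.** No earlier than randomisation or the last date known alive, whichever is later.
- **New anti-cancer therapy.** No earlier than the last study dose.
- **Progression.** No earlier than the day after the last assessment without progression.

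With these floors, the March adverse event above moves from 15 to 20 March and becomes treatment-emergent. The March death would give at least (0+1)/30.4375 = 0.03 months instead of -0.13.

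The cost is a few sentences and a small programming change. The downside is that a few pre-treatment symptoms may be counted as treatment-emergent, which is the cautious direction and matches the handling of missing causality. Imputed dates should be flagged, because an onset moved to the day of first dose could otherwise meet the same-day condition for immediate hypersensitivity in SAP Appendix 3.

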### **15.2.2.3. Dose modifications**

Dose modifications will be determined between two subsequent cycles. Variation will be calculated by comparing actual dose received.

### **15.2.2.4. overall response of the patient**

According to the revised RECIST, no confirmation of the response will be required in this phase III study to qualify the patient as CR or PR.

## **15.2.3. Date of first response and date of progression**

### **15.2.3.1. Date of first response**

The date of first response is the first date where CR, or PR is assessed. It can be found in the Tumour assessment form of the eCRF. If for the same Tumour evaluation, the assessments were made at different dates, the maximum of all the dates of assessment of the cycle will be taken into account.

### **15.2.3.2. Date of progression or death**

The date of progression is the first date where PD is assessed. The date used for PFS calculation will be the date of progression or the date of death. Date of first progression or death can be found :

In the Tumour Assessment Form of the eCRF (during the study or during the follow-up, i.e. after the end of the treatment period),,

In Death Report Form of the eCRF in case of death without “objective” progression assessed before.

If for a tumour evaluation, several assessments show a PD at different dates and the global response of the cycle is PD, the minimum of all the dates of assessment of the cycle showing PD (including appearance of new lesions) will be taken into account.

## **15.2.4. Toxicity**

### **15.2.4.1. Haematological toxicities**

The following units for HGB, WBC, PLT and ANC will be used for the analysis of haematological toxicity :

Parameters	Units
HGB	g/dl
WBC	10  /L
PLT	10  /L
ANC	10  /L

If values were expressed in different units in the CRF, the data management department will be in charge of the conversion to SI units.

Calculation of grades will be done using the following boundaries :

Grade	HGB	WBC	PLT	ANC
Grade 0	]20 – 12]	]15 – 4]	]500 – 100]	]10 – 2]
Grade 1	]12 – 10]	]4 – 3]	]100 – 75]	]2 – 1.5]
Grade 2	]10 – 8]	]3 – 2]	]75 – 50]	]1.5 – 1]
Grade 3	]8 – 6.5]	]2 – 1]	]50 – 10]	]1 – 0.5]
Grade 4	< 6.5	< 1	< 10	< 0.5

Of note, the study data manager calculates grades of haematological toxicities before database is made available to the study statistician on a read-only basis.

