5.2.2.2. Treatment modifications for haematological toxicity

Complete blood cell counts will be performed on days 1 and 8 of each cycle during the treatment period. If a patient experienced fever (temperature $\geq 38^{\circ}\text{C}$) and/or developed infection, blood cell count should be immediately performed.

Cycle delay

Cycle is considered delayed if Day 1 treatment has been performed:

- either $\geq 21 + 4$ days since last Day 1 study drug administration (i.e., Day 26 or more).
- or $\geq 14 + 4$ days since last Day 8 study drug administration

Neutrophil count should be $\geq 1.5 \times 10^9/\text{L}$ (grade 1) and platelet count $\geq 100 \times 10^9/\text{L}$ before each new cycle.

Table 5 details haematological toxicity which must result in cycle delay.

Table 5: Dose delay for haematological toxicity on day 1 of each cycle

Haematological toxicity on scheduled day 1			Day 1 administration of study treatment
Absolute neutrophils		Platelets	
$\text{ANC} \geq 1.5 \times 10^9/\text{L}$	And	$\geq 100 \times 10^9/\text{L}$	No dose modification. Treat on time
$\text{ANC} < 1.5 \times 10^9/\text{L}$	And/Or	$< 100 \times 10^9/\text{L}$	Delay one week and reassess

If recovery has not occurred after a 2-week delay, the treatment will be discontinued unless approved by the sponsor.

Dose modifications

Table 6 details haematological toxicity which must result in dose reduction.

Table 6: Dose modifications for haematological toxicity

Haematological toxicity during the previous cycle	Dose adjustment for next cycle
---	--------------------------------

Grade 3 thrombocytopenia (platelets $\geq 25 \times 10^9/L$ and $< 50 \times 10^9/L$) with significant bleeding or requiring transfusion	
First appearance : decrease one dose level
 
Second appearance : decrease one dose level
 
Third appearance : stop treatment

Grade 4 thrombocytopenia (platelets $< 25 \times 10^9/L$)	
Grade 4 neutropenia (ANC $< 0.5 \times 10^9/L$) lasting ≥ 5 days	
Neutropenic infection (grade ≥ 3 neutropenia concomitant with grade ≥ 3 infection)	
Febrile neutropenia of any grade	

5.2.2.3. *Treatment modifications for non-haematological toxicity*

Based on prior clinical experience of i.v. vinflunine, non-haematological adverse events which may require treatment modification include :

- nausea and vomiting
- constipation
- stomatitis
- and peripheral neuropathy.

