## 5.3. HAEMATOLOGICAL PARAMETERS

Haematological toxicity will be assessed by laboratory investigations of haemoglobin, WBC, ANC and platelets. Grades will be calculated according to CTCAE version 3.0.

A cycle will be evaluable for haematological toxicity analysis if the following criteria are fulfilled:

- At least one drop of any treatment,
- At least one blood cell count between Day 2 and Day 1 of next cycle or end of treatment period for the last administered cycle,
- At least one of the four haematological parameters analysed has been measured.

A patient is evaluable for haematological toxicity analysis if at least one cycle is evaluable.

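### The SAP's grading table starts platelet grade 4 below 10 x10^9/L, whereas the protocol starts it below 25, so grade 4 thrombocytopenia will be under-reported

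*SAP*

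**What the plan says.** SAP 5.3 sets the standard for haematology: "Grades will be calculated according to CTCAE version 3.0". SAP 15.2.4.1 then gives the operative rule, "Calculation of grades will be done using the following boundaries", followed by a table for haemoglobin, white cells, platelets and neutrophils in that order. Its platelet column has grade 3 running from 50 (excluded) down to 10 (included). The last row reads "Grade 4 < 6.5 < 1 < 10 < 0.5", so platelet grade 4 starts below 10 x10^9/L.

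The same section says who applies the table: "the study data manager calculates grades of haematological toxicities before database is made available to the study statistician on a read-only basis".

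The protocol (5.2) also grades toxicity by CTCAE version 3.0. Its rows for grade 3 thrombocytopenia and "Grade 4 thrombocytopenia" carry explicit counts: 25 to under 50 for grade 3, and under 25 for grade 4. These counts are the same in Table 6 (vinflunine), Table 11 (methotrexate, arm A) and Table 16 (methotrexate, arm B).

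**The concern.** One named scale cannot have two grade 4 limits for the same parameter. If the SAP table is programmed as it stands, a patient with a nadir of, say, 15 x10^9/L has grade 4 thrombocytopenia for treatment decisions under the protocol and grade 3 in the study report's laboratory tables.

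The grades feed several outputs: worst grade by patient and by cycle and the shift from baseline (SAP 11.3.1 and Appendix 1), and the myelosuppression events of special interest, which SAP Appendix 3 takes from laboratory values. Two other provisions increase the weight placed on them:

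- SAP section 13 drops the description of laboratory values over time on the ground that grades will be provided.
- SAP 11.2.1 tells the reader not to interpret haematological events from the adverse event tables. Its cross-reference to section 5.1 appears to mean the laboratory sections.

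Because the statistician receives the grades already derived, the error would not necessarily be noticed at the analysis stage.

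**Working it through.** **Inputs**

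- SAP 15.2.4.1, platelet column: grade 3 is 10 ≤ count < 50; grade 4 is count < 10.
- Protocol Tables 6, 11 and 16: grade 3 is 25 ≤ count < 50; grade 4 is count < 25.
- Scale named in both: CTCAE version 3.0 (protocol 5.2, SAP 5.3).

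**Step 1. Apply both rules to the same counts (x10^9/L)**

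| Platelet count | SAP grade | Protocol grade |
|---|---|---|
| 5 | 4 | 4 |
| 9.9 | 4 | 4 |
| 10 | 3 | 4 |
| 15 | 3 | 4 |
| 20 | 3 | 4 |
| 24.9 | 3 | 4 |
| 25 | 3 | 3 |
| 49.9 | 3 | 3 |

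Stepping through counts from 0 to 50 in units of 0.1, the rules disagree at exactly 10.0 to 24.9 and nowhere else. Reading the SAP's brackets the other way moves only the exact boundary values.

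**Step 2. Width of the disputed band**

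(25 − 10) / 25 = 15 / 25 = 60% of the protocol's grade 4 range. This is a share of the scale, not of patients.

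**Step 3. Pooled grade 3/4**

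Both rules put every count below 50 at grade 3 or higher, so pooled grade 3/4 counts are identical.

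**Step 4. Is the rest of the table off too?**

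The other cut-offs that the protocol allows one to check agree with the SAP: neutrophil grade 4 below 0.5 and grade 1 down to 1.5; transaminase bands of 2.5 to 5 and 5 to 20 times the upper limit of normal; bilirubin grade 2 at 1.5 to 3 times that limit. The platelet 3/4 boundary is the only one of these that departs. The value 10 stands in both the grade 3 and grade 4 rows, so a garbled cell does not explain it.

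**Step 5. How many patients?**

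Protocol Table 3 gives grade 3-4 thrombocytopenia for single-agent vinflunine: 2.3% at 280 mg/m² (11 of 476) and 2.7% at 320 mg/m² (29 of 1064). Applied to the 230 patients randomised to arm A:

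- 230 × 0.023 = 5.3
- 230 × 0.027 = 6.2

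The trial's starting dose is 280 mg/m², so the first figure is the relevant one: about 5 patients at grade 3-4. How many had nadirs of 10 to under 25 is not given, so under this assumption the number misgraded runs from 0 to about 5. As a share of true grade 4 cases, the loss could be anywhere from 0% to 100%.

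**The case against.** The mismatch itself is hard to contest; the case on the other side is about how much it matters.

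- **Only the split between grades 3 and 4 moves, for one of four parameters.** The listing of grade 3/4 cycles, the pooled grade 3/4 incidences and any comparison with the protocol's background table are unchanged. Overall survival is untouched, there is no formal safety stopping rule, and thrombocytopenia is not among the four events singled out for attention at the interim analysis (protocol 11.5.6.2). All of this stands.
- **The true grade is recoverable.** Individual listings carry values as well as grades. Protocol 9.1.3 also requires laboratory events that change treatment to be entered on the adverse event form, graded by CTCAE version 3.0. This softens the error but does not remove it. SAP 11.2.1 steers readers away from the adverse event tables for haematology, and the same event could then appear as grade 4 in one table and grade 3 in another.
- **SAP 5.3 points to CTCAE version 3.0, so programmers might grade correctly anyway.** Possible, but an explicit table of boundaries is what a programmer will follow. A general reference elsewhere does not override it.
- **The 5 to 6 patients do not measure the error.** Correct. That is a pooled grade 3-4 figure from single-agent use, and pooled counts do not change. It also uses randomised rather than treated patients, and the documents give no comparable rate for the combination or for arm B. It serves only as a rough ceiling under a stated assumption.

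**Conclusion.** The concern holds. The SAP's platelet boundary contradicts the protocol's grade definition although both claim the same scale, and no reason is given for the difference. Followed as written, the SAP downgrades every platelet count from 10 to under 25 x10^9/L from grade 4 to grade 3, in both arms and always towards lower severity.

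The size in patients cannot be determined from the documents. On the assumption that the combination has the single-agent rate at 280 mg/m², between 0 and about 5 arm A patients would be affected. The conclusion about under-reporting assumes that the table is programmed as printed. Its reach is limited to the separate grade 3 and grade 4 columns of the safety tables; efficacy and pooled grade 3/4 figures are unaffected.

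A minor related gap lies in the same table. Grade 0 has upper limits (haemoglobin 20, white cells 15, platelets 500, neutrophils 10), so higher counts receive no grade as written. G-CSF is permitted and dexamethasone is given before vinflunine, so high white cell or neutrophil counts are plausible. The likely effect is confined to an occasional blank cell in a baseline or shift table.

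**What to change.** In SAP 15.2.4.1, bring the platelet column into line with the protocol's grade definition: grade 3 from under 50 down to 25 inclusive, grade 4 below 25. In the same edit, remove the upper limits on grade 0 so that every measured count receives a grade. Data management should then re-derive the haematology grades before database lock. The correction has to be made there, because the statistician receives the grades ready-made. If a limit of 10 was intended, the SAP must say so, justify it, and stop describing the grades as CTCAE version 3.0 on the protocol's definition.

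The cost is one table correction and one re-run of the derivation and dependent tables. The reported grade 4 thrombocytopenia rate can only stay the same or rise. This concerns the grade used for reporting and alters no dose rule.
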